## **APPENDIX H. COLUMBIA-SUICIDE SEVERITY RATING SCALE**

- [Baseline/Screening](#)
- [Since Last Visit](#)

# COLUMBIA-SUICIDE SEVERITY RATING SCALE (C-SSRS)

Baseline/Screening Version

Version 1/14/09

*Posner, K.; Brent, D.; Lucas, C.; Gould, M.; Stanley, B.; Brown, G.; Fisher, P.; Zelazny, J.;  
Burke, A.; Oquendo, M.; Mann, J.*

*Disclaimer:*

*This scale is intended for use by trained clinicians. The questions contained in the Columbia-Suicide Severity Rating Scale are suggested probes. Ultimately, the determination of the presence of suicidality depends on clinical judgment.*

*Definitions of behavioral suicidal events in this scale are based on those used in **The Columbia Suicide History Form**, developed by [name] and [name], Conte Center for the Neuroscience of Mental Disorders (CCNMD), New York State Psychiatric Institute, [name]. (Oquendo M. A., Halberstam B. & Mann J. J., Risk factors for suicidal behavior: utility and limitations of research instruments. In M.B. First [Ed.] Standardized Evaluation in Clinical Practice, pp. 103 -130, 2003.)*

For reprints of the C-SSRS contact PPD [redacted] New York State Psychiatric Institute, [name]; inquiries and training requirements contact PPD [redacted]

SUICIDAL IDEATION		

Ask questions 1 and 2. If both are negative, proceed to "Suicidal Behavior" section. If the answer to question 2 is "yes," ask questions 3, 4 and 5. If the answer to question 1 and/or 2 is "yes", complete "Intensity of Ideation" section below.
	Lifetime: Time He/She Felt Most Suicidal	Past ___ Months

1. Wish to be Dead Subject endorses thoughts about a wish to be dead or not alive anymore, or wish to fall asleep and not wake up. Have you wished you were dead or wished you could go to sleep and not wake up?
 
If yes, describe:
	
Yes No  
	
Yes No  

2. Non-Specific Active Suicidal Thoughts General non-specific thoughts of wanting to end one's life/commit suicide (e.g. "I've thought about killing myself") without thoughts of ways to kill oneself/associated methods, intent, or plan during the assessment period. Have you actually had any thoughts of killing yourself?
 
If yes, describe:
	
Yes No  
	
Yes No  


3. Active Suicidal Ideation with Any Methods (Not Plan) without Intent to Act Subject endorses thoughts of suicide and has thought of at least one method during the assessment period. This is different than a specific plan with time, place or method details worked out (e.g. thought of method to kill self but not a specific plan). Includes person who would say, "I thought about taking an overdose but I never made a specific plan as to when, where or how I would actually do it....and I would never go through with it". Have you been thinking about how you might do this?
 
If yes, describe:
	
Yes No  
	
Yes No  

4. Active Suicidal Ideation with Some Intent to Act, without Specific Plan Active suicidal thoughts of killing oneself and subject reports having some intent to act on such thoughts, as opposed to "I have the thoughts but I definitely will not do anything about them". Have you had these thoughts and had some intention of acting on them?
 
If yes, describe:
	
Yes No  
	
Yes No  

5. Active Suicidal Ideation with Specific Plan and Intent Thoughts of killing oneself with details of plan fully or partially worked out and subject has some intent to carry it out. Have you started to work out or worked out the details of how to kill yourself? Do you intend to carry out this plan?
 
If yes, describe:
	
Yes No  
	
Yes No  

INTENSITY OF IDEATION		

The following features should be rated with respect to the most severe type of ideation (i.e., 1-5 from above, with 1 being the least severe and 5 being the most severe). For prior to study entry, ask about time he/she was feeling the most suicidal.
 
Lifetime - Most Severe Ideation: _____ Type # (1-5) Description of Ideation
 
Past X Months - Most Severe Ideation: _____ Type # (1-5) Description of Ideation
	Most Severe	Most Severe

Frequency How many times have you had these thoughts? (1) Less than once a week (2) Once a week (3) 2-5 times in week (4) Daily or almost daily (5) Many times each day
	_____	_____

Duration When you have the thoughts how long do they last? (1) Fleeting - few seconds or minutes (4) 4-8 hours/most of day (2) Less than 1 hour/some of the time (5) More than 8 hours/persistent or continuous (3) 1-4 hours/a lot of time
	_____	_____

Controllability Could /can you stop thinking about killing yourself or wanting to die if you want to? (1) Easily able to control thoughts (4) Can control thoughts with a lot of difficulty (2) Can control thoughts with little difficulty (5) Unable to control thoughts (3) Can control thoughts with some difficulty (0) Does not attempt to control thoughts
	_____	_____

Deterrents Are there things - anyone or anything (e.g. family, religion, pain of death) - that stopped you from wanting to die or acting on thoughts of committing suicide? (1) Deterrents definitely stopped you from attempting suicide (4) Deterrents most likely did not stop you (2) Deterrents probably stopped you (5) Deterrents definitely did not stop you (3) Uncertain that deterrents stopped you (0) Does not apply
	_____	_____

Reasons for Ideation What sort of reasons did you have for thinking about wanting to die or killing yourself? Was it to end the pain or stop the way you were feeling (in other words you couldn't go on living with this pain or how you were feeling) or was it to get attention, revenge or a reaction from others? Or both? (1) Completely to get attention, revenge or a reaction from others. (4) Mostly to end or stop the pain (you couldn't go on living with the pain or how you were feeling). (2) Mostly to get attention, revenge or a reaction from others. (5) Completely to end or stop the pain (you couldn't go on living with the pain or how you were feeling). (3) Equally to get attention, revenge or a reaction from others and to end/stop the pain. (0) Does not apply
	_____	_____

SUICIDAL BEHAVIOR (Check all that apply, so long as these are separate events; must ask about all types)		Lifetime		Past ___ Years	
Actual Attempt: A potentially self-injurious act committed with at least some wish to die, as a result of act . Behavior was in part thought of as method to kill oneself. Intent does not have to be 100%. If there is any intent/desire to die associated with the act, then it can be considered an actual suicide attempt. There does not have to be any injury or harm , just the potential for injury or harm. If person pulls trigger while gun is in mouth but gun is broken so no injury results, this is considered an attempt. Inferring Intent: Even if an individual denies intent/wish to die, it may be inferred clinically from the behavior or circumstances. For example, a highly lethal act that is clearly not an accident so no other intent but suicide can be inferred (e.g. gunshot to head, jumping from window of a high floor/story). Also, if someone denies intent to die, but they thought that what they did could be lethal, intent may be inferred. Have you made a suicide attempt? Have you done anything to harm yourself? Have you done anything dangerous where you could have died? What did you do? Did you _____ as a way to end your life? Did you want to die (even a little) when you _____? Were you trying to end your life when you _____? Or Did you think it was possible you could have died from _____? Or did you do it purely for other reasons / without ANY intention of killing yourself (like to relieve stress, feel better, get sympathy, or get something else to happen)? (Self-Injurious Behavior without suicidal intent) If yes, describe:		Yes No    Total # of Attempts  _____	Yes No    Total # of Attempts  _____		
Has subject engaged in Non-Suicidal Self-Injurious Behavior?		Yes No  	Yes No  		
Interrupted Attempt: When the person is interrupted (by an outside circumstance) from starting the potentially self-injurious act ( if not for that, actual attempt would have occurred ). Overdose: Person has pills in hand but is stopped from ingesting. Once they ingest any pills, this becomes an attempt rather than an interrupted attempt. Shooting: Person has gun pointed toward self, gun is taken away by someone else, or is somehow prevented from pulling trigger. Once they pull the trigger, even if the gun fails to fire, it is an attempt. Jumping: Person is poised to jump, is grabbed and taken down from ledge. Hanging: Person has noose around neck but has not yet started to hang - is stopped from doing so. Has there been a time when you started to do something to end your life but someone or something stopped you before you actually did anything? If yes, describe:		Yes No    Total # of interrupted  _____	Yes No    Total # of interrupted  _____		
Aborted Attempt: When person begins to take steps toward making a suicide attempt, but stops themselves before they actually have engaged in any self-destructive behavior. Examples are similar to interrupted attempts, except that the individual stops him/herself, instead of being stopped by something else. Has there been a time when you started to do something to try to end your life but you stopped yourself before you actually did anything? If yes, describe:		Yes No    Total # of aborted  _____	Yes No    Total # of aborted  _____		
Preparatory Acts or Behavior: Acts or preparation towards imminently making a suicide attempt. This can include anything beyond a verbalization or thought, such as assembling a specific method (e.g. buying pills, purchasing a gun) or preparing for one's death by suicide (e.g. giving things away, writing a suicide note). Have you taken any steps towards making a suicide attempt or preparing to kill yourself (such as collecting pills, getting a gun, giving valuables away or writing a suicide note)? If yes, describe:		Yes No  	Yes No  		
Suicidal Behavior: Suicidal behavior was present during the assessment period?		Yes No  	Yes No  		
Answer for Actual Attempts Only		Most Recent Attempt Date:	Most Lethal Attempt Date:	Initial/First Attempt Date:	
Actual Lethality/Medical Damage: 0. No physical damage or very minor physical damage (e.g. surface scratches). 1. Minor physical damage (e.g. lethargic speech; first-degree burns; mild bleeding; sprains). 2. Moderate physical damage; medical attention needed (e.g. conscious but sleepy, somewhat responsive; second-degree burns; bleeding of major vessel). 3. Moderately severe physical damage; medical hospitalization and likely intensive care required (e.g. comatose with reflexes intact; third-degree burns less than 20% of body; extensive blood loss but can recover; major fractures). 4. Severe physical damage; medical hospitalization with intensive care required (e.g. comatose without reflexes; third-degree burns over 20% of body; extensive blood loss with unstable vital signs; major damage to a vital area). 5. Death		Enter Code  _____	Enter Code  _____	Enter Code  _____	
Potential Lethality: Only Answer if Actual Lethality=0 Likely lethality of actual attempt if no medical damage (the following examples, while having no actual medical damage, had potential for very serious lethality: put gun in mouth and pulled the trigger but gun fails to fire so no medical damage; laying on train tracks with oncoming train but pulled away before run over).  0 = Behavior not likely to result in injury 1 = Behavior likely to result in injury but not likely to cause death 2 = Behavior likely to result in death despite available medical care		Enter Code  _____	Enter Code  _____	Enter Code  _____	

# COLUMBIA-SUICIDE SEVERITY RATING SCALE (C-SSRS)

Since Last Visit

Version 1/14/09

*Posner, K.; Brent, D.; Lucas, C.; Gould, M.; Stanley, B.; Brown, G.; Fisher, P.; Zelazny, J.;  
Burke, A.; Oquendo, M.; Mann, J.*

Disclaimer:

*This scale is intended for use by trained clinicians. The questions contained in the Columbia-Suicide Severity Rating Scale are suggested probes. Ultimately, the determination of the presence of suicidality depends on clinical judgment.*

Definitions of behavioral suicidal events in this scale are based on those used in ***The Columbia Suicide History Form***, developed by [name] and [name], Conte Center for the Neuroscience of Mental Disorders (CCNMD), New York State Psychiatric Institute, [name]. (Oquendo M. A., Halberstam B. & Mann J. J., Risk factors for suicidal behavior: utility and limitations of research instruments. In M.B. First [Ed.] Standardized Evaluation in Clinical Practice, pp. 103 -130, 2003.)

For reprints of the C-SSRS contact PPD [redacted] New York State Psychiatric Institute, [name]; inquiries and training requirements contact PPD [redacted]

SUICIDAL BEHAVIOR (Check all that apply, so long as these are separate events; must ask about all types)	Since Last Visit

Actual Attempt: A potentially self-injurious act committed with at least some wish to die, as a result of act. Behavior was in part thought of as method to kill oneself. Intent does not have to be 100%. If there is any intent/desire to die associated with the act, then it can be considered an actual suicide attempt. There does not have to be any injury or harm, just the potential for injury or harm. If person pulls trigger while gun is in mouth but gun is broken so no injury results, this is considered an attempt. Inferring Intent: Even if an individual denies intent/wish to die, it may be inferred clinically from the behavior or circumstances. For example, a highly lethal act that is clearly not an accident so no other intent but suicide can be inferred (e.g. gunshot to head, jumping from window of a high floor/story). Also, if someone denies intent to die, but they thought that what they did could be lethal, intent may be inferred.
 
Have you made a suicide attempt? Have you done anything to harm yourself? Have you done anything dangerous where you could have died? What did you do? Did you _____ as a way to end your life? Did you want to die (even a little) when you _____? Were you trying to end your life when you _____? Or did you think it was possible you could have died from _____?
 
Or did you do it purely for other reasons / without ANY intention of killing yourself (like to relieve stress, feel better, get sympathy, or get something else to happen)? (Self-Injurious Behavior without suicidal intent) If yes, describe:
	
Yes No  
 
Total # of Attempts _____
 
Yes No  


Has subject engaged in Non-Suicidal Self-Injurious Behavior?
 
Interrupted Attempt: When the person is interrupted (by an outside circumstance) from starting the potentially self-injurious act (if not for that, actual attempt would have occurred). Overdose: Person has pills in hand but is stopped from ingesting. Once they ingest any pills, this becomes an attempt rather than an interrupted attempt. Shooting: Person has gun pointed toward self, gun is taken away by someone else, or is somehow prevented from pulling trigger. Once they pull the trigger, even if the gun fails to fire, it is an attempt. Jumping: Person is poised to jump, is grabbed and taken down from ledge. Hanging: Person has noose around neck but has not yet started to hang - is stopped from doing so.
 
Has there been a time when you started to do something to end your life but someone or something stopped you before you actually did anything? If yes, describe:
	
Yes No  
 
Total # of interrupted _____

Aborted Attempt: When person begins to take steps toward making a suicide attempt, but stops themselves before they actually have engaged in any self-destructive behavior. Examples are similar to interrupted attempts, except that the individual stops him/herself, instead of being stopped by something else.
 
Has there been a time when you started to do something to try to end your life but you stopped yourself before you actually did anything? If yes, describe:
	
Yes No  
 
Total # of aborted _____

Preparatory Acts or Behavior: Acts or preparation towards imminently making a suicide attempt. This can include anything beyond a verbalization or thought, such as assembling a specific method (e.g. buying pills, purchasing a gun) or preparing for one's death by suicide (e.g. giving things away, writing a suicide note).
 
Have you taken any steps towards making a suicide attempt or preparing to kill yourself (such as collecting pills, getting a gun, giving valuables away or writing a suicide note)? If yes, describe:
	
Yes No  

Suicidal Behavior: Suicidal behavior was present during the assessment period?
	
Yes No  


Completed Suicide:
	
Yes No  

Answer for Actual Attempts Only
	
Most Lethal Attempt Date:

Actual Lethality/Medical Damage: 0. No physical damage or very minor physical damage (e.g. surface scratches). 1. Minor physical damage (e.g. lethargic speech; first-degree burns; mild bleeding; sprains). 2. Moderate physical damage; medical attention needed (e.g. conscious but sleepy, somewhat responsive; second-degree burns; bleeding of major vessel). 3. Moderately severe physical damage; medical hospitalization and likely intensive care required (e.g. comatose with reflexes intact; third-degree burns less than 20% of body; extensive blood loss but can recover; major fractures). 4. Severe physical damage; medical hospitalization with intensive care required (e.g. comatose without reflexes; third-degree burns over 20% of body; extensive blood loss with unstable vital signs; major damage to a vital area). 5. Death
	
Enter Code _____

Potential Lethality: Only Answer if Actual Lethality=0 Likely lethality of actual attempt if no medical damage (the following examples, while having no actual medical damage, had potential for very serious lethality: put gun in mouth and pulled the trigger but gun fails to fire so no medical damage; laying on train tracks with oncoming train but pulled away before run over). 0 = Behavior not likely to result in injury 1 = Behavior likely to result in injury but not likely to cause death 2 = Behavior likely to result in death despite available medical care
	
Enter Code _____

SAS	Simpson-Angus Scale
TEAE	treatment-emergent adverse event
ULN	upper limit of normal
WHO	World Health Organization

1. INTRODUCTION

This statistical analysis plan (SAP) describes the statistical methods to be used for analyses and presentation of efficacy and safety data for the study ALK3831-A305. This document has been prepared based on Alkermes [ALK3831-A305](#) Study Protocol Amendment 1.0 (dated 22 Sep 2016).

1.1. Study Objectives

1.1.1. Primary objective

The primary objective of this study is to evaluate the antipsychotic efficacy of ALKS 3831 (a fixed-dose combination of olanzapine and samidorphan) in adult subjects with an acute exacerbation of schizophrenia.

1.1.2. Secondary objective

The secondary objective of this study is to evaluate the safety and tolerability of ALKS 3831 in adult subjects with an acute exacerbation of schizophrenia.

1.2 Summary of the Study Design

[ALK3831-A305](#) is a Phase 3, multinational, multicenter, randomized, double-blind, placebo-controlled study in subjects experiencing an acute exacerbation of schizophrenia. Subjects will be screened up to 10 days prior to randomization. Upon completion of screening assessments, subjects meeting eligibility criteria will be admitted to an inpatient unit on Day -1, if they are not already inpatient. Currently prescribed antipsychotics will be discontinued at Screening.

On Day 1 (Visit 2), subjects meeting eligibility criteria will be randomized in a 1:1:1 fashion to one of the following 3 treatment groups: ALKS 3831, olanzapine, or placebo, and will receive double-blind treatment for up to 4 weeks.

On Days 1 and 2, subjects randomized to ALKS 3831 will receive 10/10 [10 mg olanzapine/10 mg samidorphan] and subjects randomized to olanzapine will receive 10 mg. On Day 3, the dose will be increased to 20/10 [20 mg olanzapine/10 mg samidorphan] for subjects randomized to ALKS 3831 or 20 mg for subjects randomized to olanzapine. Following the increase on Day 3, the dose may be decreased to 10/10 (ALKS 3831) or 10 mg (olanzapine) at end of Week 1 (Day 7) or Week 2 (Day 15) if there are tolerability problems based on judgment of the investigator. No further dose adjustments will be allowed Day 15 onward for the remaining 2 weeks of the treatment period. All subjects will receive 1 tablet daily in a blinded manner.

[figure not shown]
Subjects are required to be inpatient for the first 2 weeks of the treatment period (until Day 15). Following the mandatory 2-week inpatient stay, subjects can either continue the study as inpatients for the full 4-week treatment period or be discharged at the end of Week 2 or end of Week 3 if they meet the discharge criteria specified in [Protocol Section 8.1.1](#).

Visits during the double-blind period will be every week. Each weekly visit will consist of clinical assessments plus drug dispensing.

Subjects completing 4 weeks of treatment with study drug will be eligible to continue in the open-label, long-term safety study (ALK3831-A306) and continue to receive ALKS 3831 for up to 52 weeks. Subjects not continuing in the long term safety study will enter a 2-week Safety Follow-up Period. During this follow-up period subjects may be treated with any antipsychotic medication according to physician recommendations.

Subjects who are inpatient at the end of the 4-week treatment period and are not continuing in the extension study (ALK3831-A306) may continue as inpatients for up to 1 additional week of the 2-week safety follow-up period. These subjects may be discharged from the inpatient unit at any time during this week based on Investigator’s judgment. For subjects continuing in the safety extension study (ALK3831-A306), details regarding the additional inpatient week will be provided in the ALK3831-A306 protocol.

Figure 1: Study Design Schematic

2. SAMPLE SIZE CONSIDERATION

The planned sample size is 390 subjects in total, 130 subjects per treatment group. This sample size will provide at least 90% power to show superiority of the ALKS 3831 group compared to placebo group at a 2-sided alpha level of 0.05, assuming a 10-point improvement of PANSS total score at week 4, a standard deviation (SD) of 20, and a dropout rate of 30%.

3. DATA ANALYSIS

3.1. General Statistical Methodology

Baseline for efficacy or safety analysis is defined as the last non-missing efficacy or safety assessment on or before the first dose of study drug in the Double-blind Treatment Period.

In general, descriptive statistics: n, mean (SD), median, minimum, and maximum, for continuous variables and number and percentage of subjects in each category for categorical variables will be provided by treatment group for all variables.

All statistical tests and confidence intervals (CIs), unless stated otherwise, will be 2-sided and will be set at an alpha level of 0.05.

Unless specified otherwise, all formal comparisons will be between ALKS 3831 and placebo groups. An exploratory analysis will be conducted between olanzapine and placebo groups.

All source data will be presented as subject data listings.

3.2. Definitions of Analysis Populations

3.2.1. Safety Population

The Safety Population will include all randomized subjects who receive at least 1 dose of study drug during the double-blind treatment period. The Safety Population will be used for the safety analyses.

3.2.2. Efficacy Population

The full analysis set (FAS) will include all subjects in the Safety Population who have at least one post-baseline PANSS assessment. The FAS will be used for the efficacy analyses.

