##### **14.2.1.2. Efficacy Population**

The full analysis set (FAS) population will be used for efficacy analysis and includes all subjects in the safety population who have at least one post-baseline PANSS assessment.

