3.8.2.1. Primary Analysis

For the primary efficacy endpoint, change from baseline in PANSS total score at Week 4, primary analysis will be carried out using a mixed model with repeated measurements (MMRM) with an unstructured variance-covariance matrix based on the observed data for the FAS population. The model will include region (US vs. non-US), visit, treatment, and interaction term of visit and treatment as categorical variables, and baseline PANSS total score as a covariate. The Kenward-Roger approximation² will be used to adjust the denominator degree of freedom. The change from baseline in PANSS total score at Week 4 in the ALKS 3831 group will be compared to that in the placebo group using superiority testing at two-sided alpha level of 0.05. The least squares (LS) mean, standard error (SE), and LS mean difference between ALKS 3831 and placebo along with the 95% CI, will be summarized.

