3.8.2.2. Sensitivity Analysis

To assess the robustness of the primary analysis of the primary endpoint, the following sensitivity analyses will be performed:

- Delta-adjusted Pattern Mixture Model³ will be conducted to assess the impact of missing data. It incorporates the clinical assumption that ALKS 3831 subjects who discontinue at a given time point would have, on average, their unobserved PANSS worsened by some amount δ compared with the observed PANSS of subjects on the same treatment arm who continue to the next timepoint. Subjects who discontinue from the placebo arm would have the same PANSS trajectory as the placebo subjects who stay on the study. A sequential regression-based multiple imputation (MI) procedure will be used to incorporate the assumption and to allow uncertainty in the imputations to be reflected appropriately in the analysis. The imputation model will

include the measurement at the current timepoint as the response variable, and region (US vs. non-US) as factor, the measurements at the previous timepoints and the baseline as covariates. Twenty imputations will be carried out. For each of the 20 imputed data sets, the ANCOVA model with region (US vs. non-US) and treatment group as factors and baseline PANSS as covariate will be fitted to the change from baseline at Week 4 to obtain the treatment effect estimate and standard error. Rubin's rule will be used to combine the treatment effect estimates and standard errors across imputations. The shift parameters to be used in the sensitivity analysis will account for 10%, 20%, 30%, 40%, and 50% of the observed treatment difference between ALKS 3831 and placebo.

- The MMRM model may adjust for additional covariates and/or factors.

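### The delta-adjusted missing-data check runs by default on the FAS, so it leaves out dosed subjects who have a baseline PANSS but no post-baseline PANSS

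*SAP*

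**What the plan says.** SAP 3.2.1 sets the wider population: "The Safety Population will include all randomized subjects who receive at least 1 dose of study drug during the double-blind treatment period". SAP 3.2.2 then restricts the FAS to "all subjects in the Safety Population who have at least one post-baseline PANSS assessment. The FAS will be used for the efficacy analyses". Protocol 14.2.1.2 has the same rule; its efficacy population "includes all subjects in the safety population who have at least one post-baseline PANSS assessment".

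SAP 3.8.2.1 fits the primary MMRM "with an unstructured variance-covariance matrix based on the observed data for the FAS population". SAP 3.8.2.2 then says that a "Delta-adjusted Pattern Mixture Model³ will be conducted to assess the impact of missing data", and names no population of its own. SAP 3.8.3 plans a similar model for CGI-S, again without naming one. No efficacy analysis of all dosed or all randomised subjects is planned.

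The imputation is sequential. Each visit is regressed on region, with "the measurements at the previous timepoints and the baseline as covariates". ALKS 3831 dropouts are shifted to a worse score, while placebo dropouts are imputed like placebo subjects who stay. The shifts "will account for 10%, 20%, 30%, 40%, and 50% of the observed treatment difference between ALKS 3831 and placebo".

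Protocol Table 1 schedules post-baseline PANSS on Days 8, 15, 22 and 29, the last column also serving as the early termination visit.

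**The concern.** The delta-adjusted model is the planned test of whether the primary result survives pessimistic assumptions about dropouts. The FAS rule selects on whether post-baseline data exist, so it removes the earliest dropouts before that test begins. Nothing technical requires this. At Day 8 the imputation model needs only region and baseline, and these subjects have both.

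The direction is predictable. An excluded placebo subject would have been imputed without a shift. An excluded ALKS 3831 subject would have been shifted, possibly at every visit. Leaving the second group out lowers the average penalty on the ALKS 3831 arm. What is at stake is how hard the check tests the result, not the primary test itself.

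**Working it through.** **The plan's own figure.** SAP 2 assumes 130 per arm, a 10-point difference, SD 20, 30% dropout and two-sided alpha 0.05. Evaluable subjects per arm are 130 × 0.70 = 91. Power is Φ(10 / (20 × √(2/91)) − 1.96) = Φ(3.37 − 1.96) = 92.1%, or 91.8% with the noncentral t. The requirement is 85 evaluable per arm, and 85 / 0.70 rounds up to 122 randomised. The stated power of at least 90% is confirmed and is not in dispute.

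**Inputs for the exclusion.**
- From the SAP: 130 per arm, total dropout 30%, effect 10 points, largest shift 50%, so δ = 0.5 × 10 = 5 points.
- From Protocol Table 1: four scheduled post-baseline PANSS visits.
- Assumed: a share m of each arm is dosed but has no post-baseline PANSS, with m = 2%, 5% or 10%. The documents give no figure.
- Assumed: the 30% dropout includes m, so other dropouts are q = 0.30 − m. Before any shift the difference is 10 points in either population.

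Subjects left out per arm are 130 × m = 2.6, 6.5 or 13, so the FAS has 127.4, 123.5 or 117. Only the ALKS 3831 share enters the gap, because placebo dropouts receive no shift.

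**Formulas.**
- FAS estimate: 10 − δ × q / (1 − m)
- All dosed, shift applied once: 10 − δ × 0.30
- All dosed, shift added at all four visits for the excluded subjects: 10 − (δ × q + 4δ × m)

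**Worked case, m = 5%, δ = 5.** FAS: 10 − 5 × 0.25 / 0.95 = 8.68. Applied once: 10 − 5 × 0.30 = 8.50, a gap of 0.18. Accumulated: 10 − (5 × 0.25 + 20 × 0.05) = 7.75, a gap of 0.93.

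| m | FAS | All dosed, once | Gap | All dosed, accumulated | Gap |
|---|---|---|---|---|---|
| 2% | 8.57 | 8.50 | 0.07 | 8.20 | 0.37 |
| 5% | 8.68 | 8.50 | 0.18 | 7.75 | 0.93 |
| 10% | 8.89 | 8.50 | 0.39 | 7.00 | 1.89 |

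The gap is proportional to δ. At the 10% shift (1 point) it is 0.01-0.08 points if applied once and 0.07-0.38 if accumulated.

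**Reading the two cases.** Applying the shift once, with no carry-over, is the low case: a sequential regression on earlier visits would pass some of an early shift forward. The accumulated case carries each shift forward in full, with a slope of 1. Slopes above 1 would push an excluded subject's total past 20 points. The calculation also holds the other dropouts at a single 5-point shift; letting theirs accumulate would narrow the gap. The documents give no visit-level SDs or correlations, so neither case can be refined.

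**The case against.** The strongest objection is that the excluded group is probably small. Protocol 7.3 asks withdrawn subjects to attend an early termination visit close to the last dose, with the Visit 6 assessments, and PANSS is one of these. Any post-baseline PANSS is enough for FAS entry; it need not be the Day 8 one. Subjects are also inpatient until Day 15, so someone leaving in the first week is usually leaving a unit with study staff present. SAP 3.3 will show Safety and FAS counts by arm, so the number excluded will be visible. All of this stands, and it limits the size. It does not remove the point: Protocol 7.3 itself foresees subjects who refuse to return, and a count does not show the effect on the estimate.

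Four stronger readings are tempting, and the documents do not support them.
- A reader might infer that the FAS rule distorts the primary MMRM. Subjects with no post-baseline PANSS contribute no change score to a model of observed data, so it does not.
- A reader might multiply the excluded share by the whole accumulated shift, for instance 5% of some 22 points, and conclude that 1.1 points are hidden. That ignores the shift already applied to dropouts inside the FAS. It also needs visit SDs and a correlation that the documents do not give.
- A reader might say that these subjects' data are wholly missing. They have a baseline PANSS, which is why they can be imputed.
- A reader might extend the point to the responder analyses. SAP 3.8.5 uses LOCF there, these subjects have no post-baseline value to carry forward, and CGI-I has no baseline rating. Including them would need a new rule, which is a separate question.

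**Conclusion.** The point holds as a modest and inexpensive improvement to the sensitivity analysis. SAP 3.8.2.2 does not itself name the FAS; the population follows from SAP 3.2.2 and from the primary analysis being tested. On that reading, the analysis meant to assess missing data omits a group that its imputation model could handle, and the omission favours ALKS 3831.

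At the 50% shift the FAS estimate is more favourable by about 0.07-0.39 points if the shift is applied once, and by about 0.4-1.9 points under full additive accumulation. Both ranges rest on an assumed 10-point effect, 30% dropout and 2-10% excluded. Nothing here shows that a conclusion of the trial would change.

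**What to change.** Keep the FAS for the MMRM. In SAP 3.8.2.2 and 3.8.3, state that the delta-adjusted models use all randomised, dosed subjects with a baseline value of the endpoint (PANSS total or CGI-S). Subjects with no post-baseline value are imputed from baseline and region at the first visit, then sequentially, and shifted under the same rule as other dropouts in their arm. Report by arm the number with no post-baseline PANSS. Leave the responder analyses as they are.

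The cost is a few sentences in the SAP, a little more analysis work and a possibly slightly less favourable sensitivity result. No new data are needed, and the primary test and sample size do not change.
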